STUDY OBJECTIVES	
Primary objective
 
The primary objective is to identify more rational, pharmacologically-based drug delivery approaches to prevent nephrotoxicity from HDMTX and cisplatin and ototoxicity from cisplatin in patients with OS by:
 
 • comparing biomarkers of acute kidney injury (AKI), glomerular function and plasma and urine MTX concentrations after 12 g/m² of MTX infused over 4 and 12 hours, • comparing biomarkers of AKI, glomerular function and fractional excretion of magnesium (FEMg) after cisplatin administered with and without the OCT2 inhibitor, pantoprazole, and • comparing audiograms after cisplatin administered with and without pantoprazole. 
Secondary objectives
 
 • compare the incidence and severity (grade) of common toxicities from cisplatin/ doxorubicin administered with and without pantoprazole and from HDMTX administered as a 4 and 12 h infusion, • compare radiographic response (log ratio of tumor volumes) and histological response (percent tumor necrosis) to two cycles (10 weeks) of neoadjuvant chemotherapy for the two infusion durations of HDMTX and for cisplatin with and without pantoprazole, • correlate urinary markers of AKI and GFR estimated from serum cystatin C to standard measures of renal function (serum creatinine, urinalysis, estimated creatinine clearance, FEMg), • build a tissue microarray from biopsy, primary resection and resected metastatic tumors to evaluate the expression of proteins that are responsible for resistance

Protocol number: CHP12ST051
 Amendment number:
 Version date: April 2,, 2013

	
to the drugs in the MAP regimen and to assess expression of proteins that are targeted by new anticancer drugs under development for childhood cancers,
 
 • evaluate serum BSAP as a potential biomarker for OS, • monitor nutritional status (weight, arm circumference, skin fold thickness, pre-albumin) in patients receiving the MAP chemotherapy regimen, and • pilot an osteosarcoma-specific patient reported outcomes survey to assess the incidence and severity of tumor-related and treatment-related symptoms.
TEST ARTICLE	Pantoprazole

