1.3.3 Biomarkers of Acute Kidney Injury

Current clinical laboratory tests of renal function in children with cancer do not detect early, subtle changes in glomerular filtration rate (GFR) or renal tubular function. Limitations of serum creatinine (sCr) as a marker of GFR⁵⁷ include:

- Non-renal factors (diet, muscle mass, tubular secretion) can alter the sCr but do not affect GFR,
- sCr can be within the normal range with a GFR as low as 40 mL/min/1.73 m²,
- sCr is imprecise in small children and infants because it is rounded to the first decimal place, resulting in a significant potential error in estimating creatinine clearance (eCrCL),
- a recent change in the method used to quantify sCr has invalidated formulas used for eCrCL.⁵⁸

More sensitive and specific biomarkers to accurately quantify small changes GFR and to rapidly detect renal tubular damage are being developed. These biomarkers may be useful for detecting and monitoring renal toxicity of nephrotoxic anticancer drugs, such as MTX and cisplatin. We plan to use a panel of new biomarkers (described below) in combination with traditional laboratory tests of renal function to assess the impact of altering the schedule of HDMTX and adding pantopazole as a cisplatin rescue agent on nephrotoxicity of these drugs on this trial. These new biomarkers will include:

- **Cystatin C** is a 13kDa cysteine protease inhibitor produced by all nucleated cells. It is freely filtered, reabsorbed and metabolized in proximal tubules but not normally secreted in urine by the kidney. Serum cystatin C is used to estimate GFR and urine cystatin C is a marker of tubular damage. Cystatin C is not influenced by muscle mass, and it has improved temporal discrimination in detection of kidney injury compared to sCr. Cystatin C is measured by a FDA approved nephelometry method in clinical laboratories.⁵⁹⁻⁶⁸ CrCl can be estimated from sCr using the Schwartz formula and GFR is calculated from a sCr and Cystatin C based formula developed in the Children with Chronic Kidney Disease Cohort.⁵⁸

$$\text{CrCL} = 0.413 \cdot [\text{height (cm)}] / \text{sCr}$$

$$\text{GFR} = 39.1 \cdot \left[\frac{\text{Hgt}}{\text{Cr}_{\text{serum}}} \right]^{0.516} \left[\frac{1.8}{\text{CyC}} \right]^{0.294} \left[\frac{30}{\text{BUN}_{\text{serum}}} \right]^{0.169} [1.099]^{\text{male}} \left[\frac{\text{Hgt}}{1.4} \right]^{0.188}$$

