2. STUDY OBJECTIVES

The **primary** objective is to identify more rational, pharmacologically-based drug delivery approaches to prevent nephrotoxicity from HDMTX and cisplatin and ototoxicity from cisplatin in patients with OS by:

- comparing biomarkers of acute kidney injury (KIM-1, NAG, NGAL), glomerular function (cystatin C, creatinine) and plasma and urine MTX concentrations after 12 g/m² of MTX infused over 4 and 12 hours,
- comparing biomarkers of acute kidney injury (KIM-1, NAG, NGAL) and glomerular and tubular function (cystatin C, creatinine, FEMg) after cisplatin administered with and without the OCT2 inhibitor, pantoprazole, and
- comparing hearing loss (audiograms) after cisplatin administered with and without the OCT2 inhibitor, pantoprazole.

Secondary objectives include:

- Comparing the incidence and severity of common toxicities from cisplatin/doxorubicin administered with and without pantoprazole and from HDMTX administered as a 4 and 12 h infusion,
- comparing radiographic response (log ratio of tumor volumes) and histological response (percent tumor necrosis) to two cycles (10 weeks) of neoadjuvant chemotherapy for the two infusion durations of HDMTX and for cisplatin with and without pantoprazole,
- correlating urinary biomarkers of AKI and GFR estimated from serum cystatin C to standard measures of renal function (serum creatinine, urinalysis, estimated creatinine clearance, FEMg),
- building a tissue microarray from biopsy, primary resection and resected metastatic tumors to evaluate the expression of proteins that are responsible for resistance to the drugs in the MAP regimen and to assess expression of proteins that are targeted by new anticancer drugs under development for childhood cancers,
- evaluating serum BSAP as a potential biomarker for OS,
- monitoring nutritional status (weight, arm circumference, skin fold thickness, pre-albumin) in patients receiving the MAP chemotherapy regimen, and
- piloting an osteosarcoma-specific patient reported outcomes survey to assess the incidence and severity of tumor-related and treatment-related symptoms.

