5.1 Primary Endpoints

- Urinary biomarkers of acute kidney injury (KIM-1, NAG, NGAL) after each course of cisplatin (days 2 and 7) and each HDMTX infusion (24 h and day 7) on cycles 1-4 compared to baseline (pre-infusion) values
- Serum cystatin-C and creatinine prior to each course of cisplatin and each HDMTX infusion on cycles 1-4 and post-infusion cystatin-C and BMP if serum creatinine increases by $\geq 50\%$ compared to pre-infusion baseline value
- FEMg (simultaneous serum and spot urine for Mg and creatinine) prior to the start of the cisplatin infusions on days 1&2 and day 7 of cycles 1-4
- Plasma and urine MTX concentrations at the end of each HDMTX infusion on cycles 1-4
- Audiograms prior to cycles 1-4 and at the end of therapy.

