5.2 Secondary Endpoints

- The incidence and severity (CTCAE v.4 grade) of safety events listed in Section 5.4,
- Response of the primary tumor to the first 2 treatment cycles will be assessed by quantifying the change in tumor volume on MRI after treatment relative to the pre-treatment tumor volume using the log ratio method [$\log(V_t/V_0)$, where V_t is tumor volume post-treatment and V_0 is tumor volume at baseline]¹⁰⁹ and quantifying the percent tumor necrosis in the resected tumor specimens histologically,
- The new biomarkers of AKI (KIM-1, NAG, NGAL) and GFR (cystatin C) will be correlated with the current standard clinical laboratory methods of assessing renal function with serum creatinine, estimated creatinine clearance, urinalysis and FEMg,
- A tissue microarray will be constructed from the paraffin blocks containing the initial biopsy specimen, the resected primary tumor and resected metastatic lesion (if available) in the Pathology Core Laboratory. A slide cut from the top of the block will be used to identify areas of viable tumor, which will then be marked on the block. IHC staining will be performed for proteins responsible for resistance to MAP agents and for protein targets of new agents under development,
- Serum bone specific alkaline phosphatase will be measured at baseline, pre- and post-op, end of treatment and at the time of relapse and correlated with tumor volume,

Protocol number: CHP12ST051
Amendment number:
Version date: April 2, 2013

- An osteosarcoma-specific patient reported outcome survey (Appendix 3) developed for this study will be administered prior to each treatment cycle, prior to surgery and at the end of therapy,
- Weight, arm circumference (muscle mass), skin fold thickness (body fat), pre-albumin, and use of supplemental feedings via NG tube or G-tube will be used to assess the impact of treatment on nutritional status over the course of therapy.

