6.1 Statistical Analysis Plan

6.1.1 Primary Endpoints

- **Urinary KIM-1, NAG and NGAL** will be normalized to the urinary creatinine concentration measured in the same urine specimen and expressed as ng/mg Cr. The end of infusion and 7-day post values for each biomarker will be analyzed by course for cisplatin with vs. without pantoprazole and by dose for HDMTX administered as a 4 h vs. 12 h infusion.
- **GFR** will be estimated from serum creatinine and from the cystatin C (see Section 1.3.3) prior to each course of cisplatin and each dose of HDMTX and 7-days post treatment. A decrease in the GFR will reflect toxicity from the immediately preceding course of

Protocol number: CHP12ST051
Amendment number:
Version date: April 2, 2013

cisplatin or dose of HDMTX. Change in GFR will be analyzed by course for cisplatin with vs. without pantoprazole and by dose for HDMTX administered as a 4 h vs. 12 h infusion.

- Change in **FEMg** from pre-dose 1 (day 1 of cycles 1-4) of cisplatin to pre-dose 2 (day 2 of cycles 1-4) of cisplatin and day 7 will be measured for each cycle containing cisplatin (n=4). Change in FEMg will be analyzed by course for cisplatin with vs. without pantoprazole to assess renal tubular toxicity.
- The **urinary MTX concentration** at the end of each HDMTX infusion on cycles 1-4 will be tabulated for the 4 and 12 h infusion durations and compared to the MTX solubility limit for the urine pH to determine whether the solubility limit was exceeded. End infusion urine MTX concentration will also be correlated with simultaneous serum concentration and with the severity of renal toxicity as measured by AKI biomarkers and serum creatinine and serum cystatin C.
- An **audiogram** will be performed prior to Cycles 1, 2, 3 and 4 and at the end of therapy (after cycle 6). The average hearing level (HL) threshold in dB over the frequency range of 4,000-8,000 Hz will be derived separately for each ear from each audiogram. The increase in the average HL threshold in dB from the pre-cycle 1 to pre-cycle 2, from pre-cycle 2 to pre-cycle 3, from pre-cycle 3 to pre-cycle 4, and from pre-cycle 4 to end of therapy audiograms will be derived and this increase in HL threshold will be compared for cisplatin with vs. without pantoprazole.

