6.1.2 Secondary Endpoints

- **Common grade ≥ 2 toxicities** from cisplatin + doxorubicin (other than cisplatin nephrotoxicity and ototoxicity), including myelosuppression, mucositis, nausea and vomiting leading to dehydration requiring IV fluid hydration, peripheral neuropathy, cardiac dysfunction, and treatment delays due to toxicity will be collected and graded according to CTCAE v.4. Similarly, HDMTX-related grade ≥ 2 toxicities (other than nephrotoxicity), including myelosuppression, mucositis, dermatitis, hepatotoxicity and neurotoxicity will be collected and graded. The incidence and severity (grade) of toxicities will be tabulated and compared by treatment arm (with vs. without

pantoprazole for cisplatin + doxorubicin and by infusion duration for HDMTX).

- **Response** to 2 cycles of neoadjuvant chemotherapy will be assessed radiographically and histologically.
 - The volume of the tumor on MRI will be measured pretreatment and pre-operatively (post-cycle 2). The log ratio (Section 5.2) of the two measurements will be derived and compared using a non-parametric analysis for cisplatin with (patients on treatment arms 1 and 3) vs. without (patients on treatment arms 2 and 4) pantoprazole and for HDMTX administered as a 4 h infusion (treatment arms 1 and 2) vs. a 12 h infusion (treatment arms 3 and 4).
 - The tumor specimen that is removed after 2 cycles of neoadjuvant chemotherapy will be evaluated histologically and the percent of the tumor that is necrotic will be estimated from review of multiple sections. The percent necrosis will be compared using a non-parametric analysis for cisplatin with (patients on treatment arms 1 and 3) vs. without (patients on treatment arms 2 and 4) pantoprazole and for HDMTX administered as a 4 h infusion (treatment arms 1 and 2) vs. a 12 h infusion (treatment arms 3 and 4).
- **GFR** estimated from serum creatinine using the modified Schwartz formula will be correlated with GFR estimated from serum cystatin C (Section 1.3.3, the equation also includes serum creatinine and BUN). The presence and amount (normalized to creatinine concentration) of biomarkers of AKI in urine will be correlated with proteinuria, serum creatinine, and change in FEMg.

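### The correlation of Schwartz GFR with the cystatin C GFR in Section 6.1.2 is partly built in, because height/creatinine is in both, so read alone it cannot show whether cystatin C tracks standard renal measures

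*Combined protocol and SAP*

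**What the plan says.** The objective is the same in the Synopsis and in Section 2, where it reads "correlating urinary biomarkers of AKI and GFR estimated from serum cystatin C to standard measures of renal function". Section 5.2 states the endpoint more broadly: "GFR (cystatin C) will be correlated with the current standard clinical laboratory methods of assessing renal function". It names serum creatinine, estimated creatinine clearance, urinalysis and FEMg as the comparators.

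Section 6.1.2 turns this into analyses. GFR from serum creatinine (modified Schwartz) "will be correlated with GFR estimated from serum cystatin C (Section 1.3.3, the equation also includes serum creatinine and BUN". The next sentence covers the urinary markers only: "biomarkers of AKI in urine will be correlated with proteinuria, serum creatinine, and change in FEMg".

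Section 1.3.3 supplies the equations. The Schwartz estimate is 0.413 × height/creatinine. For the other, "GFR is calculated from a sCr and Cystatin C based formula"; the equation is

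39.1 × (Hgt/Cr)^0.516 × (1.8/CyC)^0.294 × (30/BUN)^0.169 × 1.099^male × (Hgt/1.4)^0.188.

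Serum cystatin C itself also appears in Section 6.1.1, where end-of-infusion urine MTX is to be correlated "with the severity of renal toxicity as measured by AKI biomarkers and serum creatinine and serum cystatin C". That relates it to drug concentration, not to a standard renal test. Section 5.1 lists the raw measurements among the primary endpoints: "Serum cystatin-C and creatinine prior to each course of cisplatin and each HDMTX infusion on cycles 1-4".

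**The concern.** Section 1.3.3 introduces cystatin C because serum creatinine has known weaknesses, and Section 5.2 groups it with the new markers. A reader will therefore take the correlation in Section 6.1.2 as evidence on whether cystatin C follows the standard measures. Both sides of that correlation contain height/creatinine, which has the largest exponent in the estimate named after cystatin C. The two estimates would move together even if cystatin C carried no information about the kidney.

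Section 6.1.2 specifies no other correlation between serum cystatin C and a standard renal measure, and does not carry the wider comparator list of Section 5.2 through for it. What is at stake is interpretation: a high coefficient could be reported as support for cystatin C when shared creatinine produced much of it.

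**Working it through.** The documents state no expected correlation or power for this analysis, so there is no planned figure to reproduce.

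**Inputs from Section 1.3.3.** Exponent on height/creatinine: 1 in Schwartz, 0.516 in the second equation. In the second equation only: cystatin C 0.294, BUN 0.169, male factor 1.099.

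**Inputs assumed.** Log-scale SDs of 0.10 to 0.30 for creatinine and cystatin C, and 0.20 to 0.40 for BUN. Cystatin C and BUN are taken as unrelated to creatinine, to isolate the part that arises from shared terms alone.

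**Step 1: is there a built-in part? (No assumption needed.)** Raise creatinine by 25% and hold everything else fixed.
- Schwartz: 1/1.25 − 1 = −20%.
- Second estimate: 1.25^(−0.516) − 1 = −11%.

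Both fall with cystatin C unchanged, so the shared component exists and is positive.

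**Step 2: how large could it be?** Hold height and sex constant, as for repeated values in one patient, and work on the log scale:

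r = 0.516·s_cr / √[(0.516·s_cr)² + (0.294·s_cys)² + (0.169·s_bun)²]

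| s_cr, s_cys, s_bun | r |
|---|---|
| all equal | 0.516/√(0.2663 + 0.0864 + 0.0286) = 0.84 |
| 0.15, 0.25, 0.40 | 0.61 |
| 0.10, 0.30, 0.40 (lowest) | 0.0516/√(0.00266 + 0.00778 + 0.00457) = 0.42 |
| 0.30, 0.10, 0.20 (highest) | 0.1548/√(0.02396 + 0.00086 + 0.00114) = 0.96 |

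In the equal-SD case, creatinine supplies 0.2663/0.3813 = 70% of the log variance of the second estimate, cystatin C 23% and BUN 7%. For values compared across patients, adding the sex term with 50% male puts 0.25·(ln 1.099)² = 0.0022 under the root. The range becomes 0.39 to 0.92. Under the same assumptions the correlation of 1/cystatin C with Schwartz GFR is 0.

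**Step 3: does the coefficient separate a poor marker from a good one?** With equal log-SDs and BUN independent, let ρ be the true log-scale correlation of cystatin C with creatinine:

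r = (0.516 + 0.294ρ)/√(0.3813 + 2·0.516·0.294·ρ)

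This gives 0.84, 0.88 and 0.92 for ρ = 0, 0.3 and 0.6. In this case the coefficient changes little as the marker goes from uninformative to fairly good.

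**Step 4: what would the added analysis deliver?**
- By footnote 10 of the Schedule and the table in Section 4.1, paired values per patient are baseline 1 + days 1, 7, 22 and 29 × 4 cycles = 16 + pre-op 1 + cycle 5 day 1 = 19.
- The Schedule table also marks cystatin C at end of therapy, which makes 20.
- Within-patient degrees of freedom with 24 complete patients are 24 × 18 − 1 = 431 or 24 × 19 − 1 = 455.
- The Fisher z 95% interval for r = 0.5 is about 0.43 to 0.57 either way.
- If serial correlation cut 431 to a quarter (assumed), it would be about 0.34 to 0.63.

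**The case against.** **The overlap is disclosed, and the analysis matches the objective's wording.** This stands in part. Section 1.3.3 calls the equation a creatinine and cystatin C formula, and Section 6.1.2 repeats that creatinine and BUN are in it. The objective names GFR estimated from cystatin C, not the raw marker. A reader might infer that the overlap was missed, or that 1/cystatin C should replace the planned analysis; the documents support neither. But disclosure supplies no adjustment, no reference value for r and no analysis free of creatinine on one side.

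**Section 5.2 already promises wider comparisons.** It does, so it would be wrong to say that the plan as a whole offers cystatin C only this one comparison. The gap is that Section 6.1.2, where the analyses are specified, is narrower than Section 5.2.

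**The size rests on assumptions.** This stands. The plan does not say whether the correlation is on the log scale, within patients or across them, or how repeated values are handled. The figures above are therefore not a forecast of the trial's coefficient. Complete independence of cystatin C and BUN from creatinine is a limiting case, and 0.84 is one illustration within a wide range.

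**It is only a secondary description, and the raw data will be collected anyway.** Also true. That limits the weight of the point, but writing the analysis down beforehand settles which coefficient will support the claim.

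**Conclusion.** The point holds as a limit on interpretation. The planned correlation shares height/creatinine on both sides, so alone it cannot show whether cystatin C tracks standard renal measures. Presence and sign follow from the protocol's equations. The size does not: about 0.4 to 0.96 is an illustration that depends on the assumed SDs, on independence and on constant height.

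A reader might go further and infer that the primary results are affected. They are not. The treatment comparisons do not use this coefficient, raw serum cystatin C is already among the primary measurements, and the urinary-marker correlations do not use the combined equation. The objective concerned is secondary and descriptive, with no test, power claim or decision rule attached. The change is worth making because it is cheap, not because the trial depends on it.

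**What to change.** In Section 6.1.2:

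1. Keep the planned correlation as descriptive, and label the Section 1.3.3 estimate a combined creatinine-cystatin C GFR.
2. Add the correlation of 1/serum cystatin C with Schwartz GFR, using a repeated-measures correlation on the paired samples already scheduled. Footnote 10 of the Schedule already calls for a BMP drawn with each cystatin C sample.
3. Base any statement about cystatin C's agreement with standard measures on the added analysis.
4. Optionally, also correlate 1/cystatin C with the measured 12 to 24 h creatinine clearance where samples are already paired.

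While editing, reconcile the end-of-therapy cystatin C draw, which is in the Schedule table but not in footnote 10 or Section 4.1.

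The cost is SAP wording, with no new samples or visits. There are two downsides: the reported correlation will probably be lower, and a common decline over cycles can still contribute to it.

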6.2 Sample Size and Power

The primary endpoints are sensitive urinary biomarkers of AKI and audiograms, and all endpoints are continuous variables. The study is designed to detect a signal sufficient to justify a randomized trial that would be conducted in a cooperative group setting.

Twenty-four patients will be enrolled and data will be analyzed by dose or treatment cycle with patients serving as their own control. Over the past 5 years 57 newly diagnosed patients with osteosarcoma were seen and treated at CHOP. This is an average of 11.5 patients per year, indicating that we can complete accrual to this study in about two years.

Protocol number: CHP12ST051
Amendment number:
Version date: April 2, 2013

- For the analyses of nephrotoxicity using biomarker endpoints of AKI (Urinary KIM-1, NAG and NGAL), data will be analyzed by course or by dose. Each patient will have 2 courses of cisplatin with pantoprazole and 2 courses without pantoprazole. A power calculation was conducted under the framework of a multivariate general linear hypothesis for general linear models, using the Wilks Lambda test with a significance level of 0.05.^{110,111} Because the comparison will be within subject, a larger within-subject correlation will provide greater power for the test. Based on the most conservative assumption that all repeated measures are independent, we will have 80% power to detect a 0.60SD difference for with vs. without pantoprazole. Assuming a moderate correlation of 0.5, we will have 80% power to detect a smaller difference of 0.42SD. Variability (SD) for these biomarkers in children with AKI are not available, but in a healthy adult population,¹¹² the mean value of KIM-1 was 0.228 with a SD of 0.094, so assuming a similar mean and SD for pediatric patients, we will have 80% power to detect a 0.056 difference (about 25% decrease) in the mean KIM-1 value with pantoprazole, assuming independence among repeated measures. We will have 80% power to detect a difference of 0.039 (about 17% decrease) if the correlation is moderate (e.g. 0.5).
- For comparison of HDMTX infusion durations, each patient will have 4 doses with 4 h infusion duration and 4 doses with 12 h infusion duration. Using the Wilks Lambda test with a significance level of 0.05 under the framework of general linear models, with 24 subjects of 8 repeated measures (4 measures with 4 h duration and 4 measures with 12 h duration), we will have 80% power to detect a 0.42SD difference assuming a within-subject correlation of 0, and will detect a 0.30SD difference assuming a correlation of 0.5.
- For the analyses of ototoxicity data (hearing level thresholds from 4 to 8 kHz in dB), treatment cycle will be the analysis unit. Each patient will have 2 cycles with pantoprazole and 2 cycles without pantoprazole. Using the Wilks Lambda test with a significance level of 0.05 under the framework of general linear models, with 24 subjects of 4 repeated measures (2 measures with and 2 measures without pantoprazole), we will have 80% power to detect a 0.60SD difference assuming a within-subject correlation of 0, and will detect a 0.42SD difference assuming a correlation of 0.5. Moreover, if differential carryover is present, we will only use the data from the first two cycles, so that the comparison will be between subjects, with 12 subjects in each comparison group. We will then have 80% power to detect a 1.2SD difference, based on a two-sided, two-sample t test with a significance level of 0.05.

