1.3.4 Ototoxicity

Cisplatin causes dose- and schedule-dependent permanent, sensorineural hearing loss by damaging cochlear hair cells.⁸⁷ Initially, osteosarcoma patients experience high frequency hearing loss at 4 to 8 kHz at cumulative doses exceeding 300 mg/m², but hearing at lower frequencies becomes impaired as the cumulative dose increases, and a substantial fraction of patients are affected.^{14,88-90} Younger patients are at greater risk for hearing loss from cisplatin.^{91,92} With long-term follow-up, there may be worsening or progression of hearing loss at lower frequencies.⁹³

Fractionating the cisplatin dose appears to lessen the risk of ototoxicity,⁸⁸ but more effective strategies to prevent damage to the hair cells are needed. Sodium thiosulfate is being tested as a rescue agent in an ongoing COG trial, but thiosulfate is a non-selective rescue agent and can interfere with the anti-tumor effect of cisplatin. Cochlear hair cells also express OCT2, and inhibition of OCT2 during cisplatin therapy may selectively block the uptake of cisplatin into hair cells without impacting the drug's anti-tumor effect.^{48,50}

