- **Pantoprazole** 0.3 mg/kg IV over 15 min immediately prior to cisplatin as a loading dose on days 1 & 2 followed by 1.3 mg/kg IV infused over 4 h concurrent with the 4 h cisplatin infusion on days 1 & 2 of treatment Cycles 1 & 2 (Treatment Arms 1, 3) OR Cycles 3 & 4 (Treatment Arms 2, 4);
- **CISplatin** 60 mg/m²/dose infused IV over 4 h on days 1 & 2 (total dose 120 mg/m²/cycle) of treatment cycles 1-4;
- **Pegfilgrastim** 0.1 mg/kg (6 mg for patients weighing ≥45 kg) SC on day 3 or 4 of treatment cycles 1-6;
- **Methotrexate** 12 g/m² (maximum dose 20 g) infused IV over 4 OR 12 h on days 22 & 29 of Cycles 1-4 and on days 15 and 22 of Cycles 5 & 6 (HDMTX infusion duration on Cycles 5 & 6 based on patient tolerance on cycles 1-4);
- **Leucovorin** 15 mg/m² IV or PO every 6 h until serum MTX <0.1 mcM on days 23 and 30 of cycles 1-4 and days 16 & 23 of cycles 5 & 6, **starting 24 h after the start of the HDMTX infusion.**

Intravenous fluid hydration guidelines: Intravenous fluid hydration should be administered prior to, during and after cisplatin and HDMTX. In addition, the urine should be alkalinized to a pH of ≥7 for HDMTX until serum MTX <1 mcM by including sodium bicarbonate or equivalent base in the IV fluids.

Cisplatin:

- Prior to the first dose of cisplatin on day 1 of the cycle, infuse a normal saline (0.9% NaCl) fluid bolus of 750 mL/m² over 1 h.
- Cisplatin is diluted in 0.9% NaCl to a final cisplatin concentration of 100 mg/L. Therefore,

patients will receive 150 mL/m²/h of this solution over the 4 hour drug infusion.

- After the cisplatin infusion is completed, infuse 100 mL/m²/h D₅ 0.45% NaCl + 20 mEq/L KCl until at least 12 h after the second cisplatin infusion is completed and the patient is tolerating PO fluids.
- Monitor Input and Output, at 3hr or 6hr after start of cisplatin
 - If urine Output > total Input by 100 mL/m²/hr over the previous 3 hr, consider 0.9% NaCl bolus (10-15 cc/kg)
 - If total Input > urine Output by 100 mL/m²/hr over the previous 3 hr, consider furosemide (0.5 mg/kg, MAX dose 20 mg) to promote urine output.^{104,105}

HDMTX:

- Prior to the start of a HDMTX infusion, infuse D₅ 0.22% NaCl with 40 mEq/L NaHCO₃ (sodium bicarbonate) or equivalent base as a fluid bolus of 750 mL/m² over 1 h.

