3.2 Randomization

Patients will be randomized to one of 4 treatment arms (see Study Diagram), which will determine the order in which they receive pantoprazole with cisplatin (Cycles 1&2 vs. Cycles 3&4) and the order in which they will receive HDMTX as a 4 or 12 h infusion (Cycles 1&2 vs. Cycles 3&4). A block randomization procedure will be used so that 3 of the first 12 subjects will be randomly assigned to each of the 4 treatment arms (three patient per arm) and 3 of subjects 13 to 24 will be randomly assigned to each of the 4 arms (six patients per arm when enrollment is completed). Subjects who are unable to complete 4 cycles of therapy may be replaced, and the new subject will be placed on the same treatment arm as the subject being replaced.

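### The 80% hearing power assumes the same pantoprazole effect in all four cycles, but by the protocol's own onset dose the first crossover block carries little or no hearing information

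*Combined protocol and SAP*

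**What the plan says.** - **Endpoint.** Section 6.1.1 averages the hearing threshold over 4,000-8,000 Hz and takes the increase from one audiogram to the next. It then says that "this increase in HL threshold will be compared for cisplatin with vs. without pantoprazole". Audiograms are among the primary endpoints (section 5.1).
- **Power.** Section 6.2 takes 24 subjects with two cycles on and two cycles off pantoprazole and concludes that "we will have 80% power to detect a 0.60SD difference assuming a within-subject correlation of 0, and will detect a 0.42SD difference" at a correlation of 0.5. It gives no effect in dB, no SD in dB and no dose-response.
- **Onset of loss.** Section 1.3.4, on the same frequency band: "Initially, osteosarcoma patients experience high frequency hearing loss at 4 to 8 kHz at cumulative doses exceeding 300 mg/m²".
- **Dose.** Section 3.1.3 gives cisplatin as "60 mg/m²/dose infused IV over 4 h on days 1 & 2 (total dose 120 mg/m²/cycle) of treatment cycles 1-4". Under section 3.2 pantoprazole is given in cycles 1-2 or in cycles 3-4, in random order.
- **Carryover.** Section 6.1.1 accepts that hearing may carry over, but expects this not to differ between the arms because the order is randomized. If differential carryover is found, section 6.1.1 keeps cycle 1 only. Section 6.2 keeps the first two cycles, with 12 patients per group and 80% power for 1.2 SD.

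**The concern.** The dose schedule and the onset statement are never set beside each other. At 120 mg/m² per cycle, cumulative dose is 120 and 240 mg/m² in block 1, then 360 and 480 mg/m² in block 2. The 300 mg/m² mark is passed during cycle 3. If loss in this band starts there, block 1 shows little or nothing with or without pantoprazole, yet it supplies half of the crossover contrast.

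Section 6.2 says that the study should find a signal strong enough to justify a cooperative-group trial. A null hearing result read against a stated 80% power could be taken as evidence that pantoprazole does not protect hearing, when the comparison may have had little chance of showing protection.

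**Working it through.** **1. The plan's figures.** The contrast is the mean of two cycles with pantoprazole minus the mean of two without, so SE = SD × √((1 − ρ)/24). A two-sided t test at 0.05 with 23 df (22 df with a sequence term) gives:
- 0.60 SD, ρ = 0: noncentrality 0.60 × √24 = 2.94, power 80.4% (80.2%).
- 0.42 SD, ρ = 0.5: 0.42 × √(24/0.5) = 2.91, power 79.6% (79.4%).
- Fallback, 1.2 SD with 12 per group: 1.2 × √6 = 2.94, 22 df, power 80.2%.

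All three reproduce.

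**2. Set-up.** Let f(d) be cumulative loss in dB at cumulative dose d, and let p be the share of the effect that pantoprazole blocks. Taking section 1.3.4 literally, f(d) = 0 up to 300 mg/m². Contrasts are per cycle, with minus without, averaged over the two orders, which removes the period effect.

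**3. Loss follows cumulative unshielded exposure.**
- Pantoprazole first: exposure is 240(1 − p) after block 1 and 480 − 240p after block 2.
- Pantoprazole second: exposure is 240 after block 1 and 480 − 240p after block 2.
- Write E = f(480 − 240p). The with-minus-without difference is [2f(240(1 − p)) − E]/2 in the first order and [E − 2f(240)]/2 in the second.
- The average is [f(240(1 − p)) − f(240)]/2. E cancels because both orders end at the same exposure, so only block 1 matters.
- With f(240) = 0 the contrast is 0 for every p, and power equals the 5% significance level.

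**4. Pantoprazole reduces only the current cycle's loss.**
- Block 1 is zero in both orders. Let u be the mean per-cycle loss in block 2 without pantoprazole.
- Pantoprazole first: 0 − u = −u. Pantoprazole second: (1 − p)u − 0.
- The average is −pu/2, half of the block 2 difference pu.
- A block 2 difference of 0.60 SD gives 0.30 SD: noncentrality 0.30 × √24 = 1.47, power 29%. At ρ = 0.5, 0.42 SD in block 2 gives 0.21 SD and also 29%.
- For 80% power the block 2 difference must be 2 × 0.597 = 1.2 SD, or 2 × 0.422 = 0.84 SD at ρ = 0.5.

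**5. If loss starts earlier.** Assumptions: full protection, loss linear in dose above the onset, equal SD in all cycles, ρ = 0, and a slope that would give the planned 0.60 SD if loss began with the first dose.

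| Onset (mg/m²) | Power, cumulative unshielded exposure | Power, current cycle only |
|---|---|---|
| 300 | 5% | 18% |
| 180 | 11% | 42% |
| 120 | 29% | 56% |
| 0 | 80% | 80% |

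The 18% is lower than the 29% in step 4 because, on this slope, cycle 3 contributes only the 60 mg/m² above the onset. The contrast is then 45/120 = 37.5% of the planned one, or 0.225 SD.

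**6. Carryover and fallback.** Randomizing the order balances patients between the orders. It does not stop shielding in block 1 from changing what happens in block 2 in one order only. Both fallback data sets, cycle 1 (up to 120 mg/m²) and cycles 1-2 (up to 240 mg/m²), lie below the onset, so little difference is expected in either.

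**The case against.** A reader might infer that the hearing contrast is about zero whatever pantoprazole does, or that the 80% power is a miscalculation. The documents support neither.

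- **The zero depends on a model.** It needs loss to follow cumulative unshielded exposure. Section 1.3.4 suggests a block on uptake into hair cells, which makes this plausible, but no dose-response is stated. Under the current-cycle model block 2 carries a real randomized contrast, and power can be high if the dB effect is large. Assume a 300 mg/m² onset, 30 dB of loss at 480 mg/m² and an SD of 5 dB. The contrast is then p × 30/4, or 7.5, 3.75 and 1.9 dB at p = 1, 0.5 and 0.25, with power of about 100%, 94% and 42%. None of these dB inputs is in the documents.
- **Section 1.3.4 describes typical onset.** It does not say that the mean shift is zero below 300 mg/m², and the endpoint is continuous. Under the cumulative model with full protection and an SD of 5 dB, a mean shift of 6 dB by 240 mg/m² gives a contrast of 3 dB and 80% power; a shift of 3 dB gives 29%.
- **The power statement is conditional and correct in SD units.** This is also a pilot, and section 6.1.1 already admits limited power for the carryover test.

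These points stand, and they limit the claim to a range. They do not justify equal effects in all four cycles, which section 6.2 assumes without saying so and which does not fit the onset dose in section 1.3.4.

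**Conclusion.** The concern holds in conditional form and should be fixed. If loss in this band starts at 300 mg/m², block 1 carries little or no hearing information. Power is then about 5% under cumulative unshielded exposure and about 29% for a 0.60 SD effect confined to block 2. It reaches 80% only if the block 2 difference is about 1.2 SD (0.84 SD at correlation 0.5). Earlier onset or a large dB effect in block 2 would improve this.

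The SD-scale results assume equal SD in all cycles and no dropout or early end of cisplatin; the table also assumes linear loss above the onset. It would be wrong to state 5% as the trial's power: that is one end of a range whose position the documents do not settle. What they lack is support for 80% as an unqualified figure.

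**What to change.** 1. **Section 6.2:** state that the 0.60 and 0.42 SD figures assume equal effects in all four cycles. Give the range under a 300 mg/m² onset with its assumptions: about 5% under cumulative unshielded exposure, and about 29% for a 0.60 SD effect confined to block 2.
2. **Section 6.1.1:** state that a null hearing crossover result is not evidence of no protection.
3. **Section 6.1.1:** keep the randomized crossover comparison and also report the with-versus-without difference by block, including the comparison between orders in cycles 3-4. Say that the block 2 comparison is between patients, less precise, and affected by what was given in block 1.
4. **Sections 6.1.1 and 6.2:** reconcile the two fallback rules (cycle 1 against the first two cycles), and state that either one tests only doses up to 240 mg/m².
5. Report the change from baseline to end of therapy only as a descriptive supplement. Every patient has two courses with and two without pantoprazole, so this summary has no internal control and should not replace the randomized contrast.

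The cost is protocol and SAP wording plus a few extra analyses of data already collected. The downside is a less favourable stated power for hearing.
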